Research Title: Construction and Clinical Validation of a Predictive
Model for Postoperative Adjuvant Therapy in Hepatocellular Carcinoma
Based on Whole-Slide Digital Pathological Images and Deep Learning

NCT Number: NCT07417800

Document date: 2025/10/24

Research Protocol

Study Background

Hepatocellular Carcinoma (HCC) is one of the most common malignant tumors worldwide, ranking sixth in incidence and third in mortality globally, causing approximately 480,000 deaths each year. China accounts for more than 45% of global HCC cases, resulting in an extremely heavy disease burden. Curative surgical resection is the primary approach to achieve long-term survival for patients with early-stage HCC. However, the postoperative recurrence rate reaches 50%–70% within five years after surgery, which seriously impairs patient prognosis. Postoperative adjuvant therapy has become a key strategy to delay tumor recurrence and improve survival outcomes. Transarterial Chemoembolization (TACE) and Tyrosine Kinase Inhibitors (TKIs), such as sorafenib and lenvatinib, are widely applied for patients at high recurrence risk after surgery.

Nevertheless, both treatment modalities have notable limitations. The objective response rate of TACE is merely 50%–60%; a considerable number of patients fail to benefit from this therapy and may suffer from treatment-induced liver function injury. Although TKIs can prolong recurrence-free survival (RFS) by 3 to 5 months in high-risk postoperative HCC patients, the treatment response rate is less than 20% in unselected populations. Additionally, the incidence of Grade 3–4 adverse events including hypertension, hand-foot skin reaction and proteinuria exceeds 50%, leading to treatment discontinuation in around 20% of patients due to intolerable toxicities. Currently, there is a lack of efficient and reliable biomarker systems to identify patients who may benefit from treatment. Clinical treatment decisions still rely on empirical judgment based on conventional pathological features such as tumor size and vascular invasion, resulting in insufficient individualized treatment, wasted medical resources and additional treatment burdens on patients.

Recent studies have demonstrated that the Tumor Immune Microenvironment (TIME) is a fundamental biological factor affecting the sensitivity to TACE and TKIs in HCC patients. Preoperative contrast-enhanced CT/MRI can directly reflect tumor vascularity, boundary definition, peritumoral infiltration and satellite lesions. These imaging characteristics are closely correlated with postoperative pathological findings including Microvascular Invasion (MVI) and tumor differentiation, and further determine responses to adjuvant therapy. For example, preoperative MRI radiomic features such as textual heterogeneity and irregular tumor margins have been proven to be significantly associated with postoperative HCC recurrence risk. Moreover, CT perfusion parameters can predict the degree of tumor necrosis after TACE treatment. Furthermore, the combination of preoperative imaging and postoperative pathological images enables the construction of tumor spatiotemporal evolution models to reveal dynamic biological changes before and after therapeutic intervention. Therefore, multimodal data integrating preoperative imaging, postoperative pathological images, pathological reports and clinical indicators can break the limitations of single-source data and substantially improve the accuracy of adjuvant therapy response prediction.

Breakthroughs in artificial intelligence, especially deep learning technology, have opened up a new avenue to explore in-depth pathological information from routine Hematoxylin and Eosin (H&E) stained Whole Slide Images (WSIs). As conventional postoperative pathological materials, H&E WSIs are generated for all HCC patients after surgery without additional sampling or testing. The cellular and histological details contained in WSIs can effectively reflect core characteristics of the TIME. Specifically, Convolutional Neural Networks (CNN) and Vision Transformer (ViT)

architectures can automatically identify morphological patterns related to CD8⁺ T cell infiltration density and PD-L1 expression, realizing cross-modal prediction of immune status based on H&E morphological features. Latest studies have verified that deep learning models based on H&E WSIs achieve high accuracy in predicting Microsatellite Instability (MSI) in colorectal cancer (AUC = 0.88), PD-L1 expression in non-small cell lung cancer (AUC = 0.80) and Tumor Mutation Burden (TMB) (AUC = 0.91). In the field of HCC, WSI-based deep learning models have also achieved favorable performance in predicting postoperative recurrence risk (AUC = 0.82) and immune cell infiltration (AUC = 0.78). However, no studies have focused on the critical clinical issue of predicting responses to postoperative adjuvant therapy (TACE/TKIs) by integrating preoperative imaging and postoperative multimodal pathological data, and large-scale multicenter prospective clinical validation is still lacking.

Accordingly, this study aims to integrate multicenter clinicopathological data with artificial intelligence algorithms to establish a multimodal predictive model based on preoperative imaging, postoperative pathological WSIs, pathological reports and clinical indicators. It intends to clarify the correlation between preoperative tumor characteristics and responses to postoperative adjuvant therapy, develop clinically applicable digital decision-making tools, and promote the multi-dimensional and full-cycle precise management of HCC.

Study Objectives

This study aims to construct and validate a multimodal data platform by integrating preoperative contrast-enhanced CT/MRI images, postoperative H&E-stained Whole Slide Images (WSIs), pathological reports and clinical indicators collected from HCC patients across multiple centers. Radiomic feature extraction and deep learning algorithms will be adopted to develop a joint predictive model, so as to accurately identify HCC subtypes sensitive to TACE and TKIs preoperatively and quantitatively evaluate treatment efficacy. Meanwhile, this study intends to elucidate the spatiotemporal biological evolution patterns of tumors during postoperative adjuvant therapy, including vascular remodeling and dynamic changes of the tumor immune microenvironment. The predictive performance of the model will be validated in prospective cohorts, and a visual decision support system will be developed to optimize individualized postoperative adjuvant therapy strategies, reduce the rate of ineffective treatment, and advance the multi-dimensional and full-cycle precise treatment and management of hepatocellular carcinoma.

Study Design and Methods

3.1 Trial Design and Study Population

This is a comprehensive study combining diagnostic trials and interventional studies, divided into two major parts and multiple phases, aiming to develop and validate an artificial intelligence-based prediction system for postoperative adjuvant therapy of hepatocellular carcinoma (HCC). The overall study complies with the development specifications of Software as a Medical Device (SaMD) based on artificial intelligence, including retrospective data collection, model development and training, retrospective validation, prospective observational validation and final prospective interventional studies.

Part One: Retrospective Study on the Construction of Tumor Immune Microenvironment Identification and Adjuvant Therapy Prediction Model

(1) Construction and Validation of Tumor Immune Microenvironment Identification Model

Development and Training Phase

Public datasets (e.g., TCGA) and retrospective datasets from our center (n=1500, 400 cases collected so far) will be used as the training set. The core task of this phase is to develop a deep learning model (architectures such as Vision Transformer or ResNet) to automatically identify, segment and quantify key features of the tumor immune microenvironment from H&E-stained digital pathological Whole Slide Images (WSIs), including but not limited to the degree of immune cell infiltration, stroma ratio, vascular invasion and necrotic areas. Meanwhile, preoperative contrast-enhanced CT/MRI images will be integrated. Radiomic feature extraction techniques (such as texture analysis and morphological feature analysis) and deep learning algorithms will be applied to explore tumor vascularity, morphological features of tumor margins and peritumoral infiltration information, and conduct multimodal correlation analysis with pathological features. All images will be independently annotated by at least two senior physicians in a blinded manner. Any discrepancies will be resolved through consensus negotiation or arbitration by a third senior physician to form the gold standard.

External Validation Phase

Retrospective WSI and imaging datasets from 8 to 10 collaborative medical centers across China will be used to preliminarily validate the generalization ability of the model. This phase aims to evaluate the robustness of the model under different scanning devices, pathological slide preparation and staining procedures, and interpretation habits of pathologists.

(2) Construction and Multi-level Clinical Validation of Treatment Response Prediction Model

This is the core part of the study. Based on the quantified tumor immune microenvironment features output by the above model, combined with imaging data and essential clinical variables (such as TNM stage, Child-Pugh liver function classification and AFP level), a classification model will be built to predict patients' responses to four types of postoperative adjuvant therapy regimens: surgery alone, surgery combined with TACE, surgery combined with TACE plus systemic therapy, and surgery combined with systemic therapy alone. A strict hierarchical validation strategy will be adopted in this part.

Model Training Phase

Retrospective data from our center (n=1500) will be used. Inclusion criteria for patients in this phase: ① Histopathologically confirmed HCC; ② Underwent curative surgical resection; ③ Complete preoperative contrast-enhanced CT/MRI images, records of postoperative adjuvant therapy and follow-up data are available. Definition of treatment response: The primary endpoint is Relapse-Free Survival (RFS), and secondary endpoints include Overall Survival (OS) and Objective Response Rate (ORR). Multi-category machine learning algorithms (such as Gradient Boosting Decision Tree and Deep Neural Network) will be used for model training to output the most beneficial treatment regimen for each patient.

Internal Validation Phase

An independent validation set (n≈500, no overlap with the training set) will be randomly divided from the data of our center for preliminary evaluation of the model's discriminative performance and hyperparameter tuning to prevent overfitting.

External Validation Phase 1 (Retrospective Validation and Model Calibration)

Retrospective data (n=3000) will be collected from 8 to 10 medical centers nationwide. The main purposes of this phase are: ① To validate the model performance on larger and more heterogeneous external datasets; ② To calibrate or slightly optimize the model according to

validation results and finalize the predictive model.

External Validation Phase 2 (Large-scale Retrospective Validation)

The finalized model will be tested on a brand-new large-scale retrospective dataset (n=10,000) from 3 to 5 medical centers to further enhance the level of evidence and provide a solid basis for prospective studies.

(3) Study Population

The study population consists of patients who underwent curative surgical resection for HCC. Multiple datasets will be established for model development, training and validation, and all datasets will be constructed in accordance with strict inclusion and exclusion criteria.

(1) Patient Inclusion and Exclusion Criteria

Inclusion Criteria

Histopathologically confirmed diagnosis of hepatocellular carcinoma;

Aged between 18 and 75 years old;

Underwent curative resection (R0 resection) for primary hepatocellular carcinoma;

Complete postoperative formalin-fixed paraffin-embedded (FFPE) H&E-stained tissue slides eligible for digital scanning;

Complete and accessible clinicopathological data and follow-up data, including but not limited to age, gender, HBsAg status, liver cirrhosis background, AFP and PIVKA-II levels, tumor size and number, CNLC stage, AJCC 8th TNM stage, BCLC stage, vascular invasion status, tumor differentiation grade, detailed postoperative adjuvant therapy regimens and medication records, as well as postoperative tumor recurrence and survival data;

Preoperative contrast-enhanced CT or MRI images with standardized scanning parameters and no severe artifacts, meeting the requirements for analytical use.

Exclusion Criteria

Received anti-tumor treatments such as TACE, targeted therapy, immunotherapy and radiotherapy at non-collaborative medical centers before surgery, with unavailable original imaging and clinical baseline data;

Combined with primary malignant tumors of other organs;

Positive surgical margins after surgery (R1 or R2 resection);

Poor quality of pathological tissue slides (such as severe fading, folding, breakage or insufficient tissue volume), which cannot be used for digital scanning or reliable analysis;

Severe missing of clinical or follow-up data;

Missing preoperative imaging data or unqualified imaging quality (such as severe artifacts or incomplete scanning sequences) that cannot be used for analysis.

(2) Definition and Source of Datasets

A multi-center and multi-stage data collection strategy will be adopted for all datasets, which are strictly divided according to purposes to ensure mutual independence of the training set, validation set and test set and avoid data leakage.

A total of 1,500 eligible surgical patients from our center will be enrolled and randomly divided into the model training set (n=1000) and internal validation set (n=500) at a ratio of 2:1, for model training, preliminary validation and optimization respectively. A total of 400 eligible patients have been enrolled so far, and the remaining 1,100 patients will be continuously recruited from the historical medical records of our center according to the inclusion and exclusion criteria.

A multi-center collaboration model will be adopted for external validation. ① External Validation

Set 1: A total of 3,000 retrospective cases from 8 to 10 domestic medical centers will be included for multi-center retrospective validation and model calibration, so as to verify the model's generalization ability across different institutions and conduct calibration or limited iterative optimization on the initial model. ② External Validation Set 2: A total of 10,000 retrospective cases from 3 to 5 large domestic medical centers will be included for the final test of the finalized model to fully evaluate its effectiveness and stability. Only forward validation will be performed on this dataset using the locked model without any parameter adjustment.

Part Two: Clinical Validation of Hepatocellular Carcinoma Adjuvant Therapy Prediction Model - Prospective Study

(1) Prospective Observational Study

A total of 1,000 eligible postoperative HCC patients will be consecutively enrolled from 10 to 15 medical centers. Preoperative imaging data, postoperative WSIs and clinical data will be collected and imported into the model to obtain predicted treatment regimens. No intervention will be implemented on actual clinical decisions in this phase. Researchers will record model prediction results and actual clinical decisions. Patients will be divided into the prediction-consistent cohort and prediction-inconsistent cohort according to whether the actual clinical decisions are consistent with model predictions. Long-term follow-up will be conducted to observe patients' actual prognosis, so as to evaluate the consistency between model predictions and actual outcomes, as well as the model's performance degradation in real-world settings.

(2) Study Population

The study population consists of patients who underwent curative surgical resection for HCC. Multiple datasets will be established in the prospective study for model optimization and validation, and all datasets will be constructed in accordance with strict inclusion and exclusion criteria.

(1) Patient Inclusion and Exclusion Criteria

Inclusion Criteria

Histopathologically confirmed diagnosis of hepatocellular carcinoma;

Aged between 18 and 75 years old;

Underwent curative resection (R0 resection) for primary hepatocellular carcinoma;

Complete postoperative formalin-fixed paraffin-embedded (FFPE) H&E-stained tissue slides eligible for digital scanning;

Complete and accessible preoperative CT/MRI images, clinicopathological data and follow-up data, including but not limited to age, gender, HBsAg status, liver cirrhosis background, AFP and PIVKA-II levels, tumor size and number, CNLC stage, AJCC 8th TNM stage, BCLC stage, vascular invasion status, tumor differentiation grade, detailed postoperative adjuvant therapy regimens and medication records, as well as postoperative tumor recurrence and survival data;

Signed the informed consent form for the prospective study.

Exclusion Criteria

Received anti-tumor treatments such as TACE, targeted therapy, immunotherapy and radiotherapy at non-collaborative medical centers before surgery, with unavailable original imaging and clinical baseline data;

Combined with primary malignant tumors of other organs;

Positive surgical margins after surgery (R1 or R2 resection);

Poor quality of pathological tissue slides (such as severe fading, folding, breakage or insufficient

tissue volume), which cannot be used for digital scanning or reliable analysis;

Severe missing of clinical or follow-up data.

(2) Definition and Source of Datasets

A multi-center and multi-stage data collection strategy will be adopted for all datasets, which are strictly divided according to purposes to ensure mutual independence of the training set, validation set and test set and avoid data leakage.

A multi-center collaboration model will be adopted for the prospective cohort. ① Prospective Observational Cohort: A total of 1,000 patients will be consecutively enrolled from 10 to 15 medical centers. Pathological slides will be collected for digital scanning, and preoperative imaging data will be imported into the model. No clinical intervention will be conducted; only model predictions and actual clinical outcomes will be recorded to evaluate the model's performance in real clinical settings. ② Prospective Interventional Cohort: A randomized controlled trial will be carried out in 3 to 5 medical centers with a planned enrollment of 600 patients. After obtaining patients' informed consent, patients will be randomly assigned to the intervention group (AI model-assisted decision-making) and the control group (standard clinical decision-making). Physicians in the intervention group will formulate treatment plans with reference to the optimal treatment regimens predicted by the AI model; the control group will receive routine treatment. Clinical outcomes will be compared between the two groups to provide high-level evidence for the clinical utility of the model.

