Fairness assessment: Comprehensive fairness evaluation is carried out to analyze whether there are significant differences in model performance across subgroups divided by demographic characteristics (gender, age) and clinical characteristics (tumor stage, etiology, liver function classification). Core evaluation indicators include inter-group AUC difference, balanced odds and fairness metrics for sensitive attributes. If performance discrimination of the model is found in specific subgroups, algorithm correction will be performed to ensure the fairness of algorithm decisions. All fairness evaluation results will be fully disclosed in the research report.

Bias control in statistical analysis phase: Multivariate Cox regression model and Logistic regression model are used to adjust for known prognostic factors (such as TNM stage, vascular invasion and AFP level) to accurately estimate the independent predictive efficacy of the AI model and control potential residual confounding bias.

3.6 Data Governance System (Data Collection, Transmission, Storage Security Control; Full-chain Data Recording)

A sound data governance system is established to ensure the quality, security and compliance of data throughout the research process, covering all links including data collection, transmission, storage, processing, analysis and archiving, forming a complete data management closed loop.

Standardized data collection: Detailed Standard Operating Procedures (SOPs) for data collection are formulated to clarify the definition, format and collection specifications of all types of data. Structured electronic Case Report Forms (eCRFs) are used for clinical data collection with built-in logic verification and range check functions to ensure the accuracy and completeness of data collection. Pathological image data collection follows digital scanning standards with a unified scanning resolution of 0.25 μ m/pixel and file format of SVS. Equipment calibration and quality control tests are conducted before each batch of scanning. Laboratory test data are directly collected by docking with the Laboratory Information System (LIS) to avoid manual transcription errors.

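### As written, the 500 internal-validation patients also train the upstream microenvironment model and tune the response model, so the internal figures are not independent; and later model changes are not reconciled with the lock before External Validation Set 2

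*Protocol*

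**What the plan says.** All of this is in the Protocol.

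- **Microenvironment model** (3.1, Part One (1), Development and Training Phase): public data and "retrospective datasets from our center (n=1500, 400 cases collected so far) will be used as the training set". The only validation named for this model is external; no internal hold-out is mentioned.
- **Response model** (3.1, Part One (2)): it is built "Based on the quantified tumor immune microenvironment features output by the above model", together with imaging and clinical variables. Its Model Training Phase states "Retrospective data from our center (n=1500) will be used". The Internal Validation Phase then draws about 500 patients from the same centre, described as independent and not overlapping with training.
- **Role of the 500**: preliminary evaluation of "discriminative performance and hyperparameter tuning to prevent overfitting".
- **Dataset definition** (3.1, Part One (3)): the 1,500 centre patients, 400 of them already enrolled, are "randomly divided into the model training set (n=1000) and internal validation set (n=500) at a ratio of 2:1". The same section commits to mutually independent training, validation and test sets and to avoiding leakage.
- **External sets** (3.1, Part One (2) and (3)): External Validation Set 1 (3,000 patients) may be used to calibrate or slightly optimise the model, which is then finalised. Set 2 (10,000 patients, described as entirely new data) is run "using the locked model without any parameter adjustment" and is meant to support the prospective studies.
- **After Set 2** (3.1, Part Two (2)): "Multiple datasets will be established in the prospective study for model optimization and validation".
- **Fairness** (3.5): if the model performs discriminatorily in particular subgroups, "algorithm correction will be performed to ensure the fairness of algorithm decisions". Neither a phase nor a re-validation is given.

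**The concern.** A hold-out set gives an honest performance estimate only if nothing in the prediction pipeline has been fitted to it. Here the pipeline has two stages. If stage one has seen the 500, the features it supplies for them may be cleaner than those it would supply for new patients, and stage two is then scored on inputs of a quality that will not recur. Choosing hyperparameters on the 500 and reporting discrimination on the same 500 adds selection optimism, whatever is decided about stage one.

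At stake is what the internal result may be called, and the tuning choices that rest on it.

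The second issue is version control. The validation evidence belongs to the version that was finalised and tested on Set 2. If that version is later optimised or corrected, the version guiding treatment decisions in the 600-patient randomised trial need not be the one to which the evidence applies.

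**Working it through.** **Inputs.** Centre patients available: 1,500. Microenvironment training cases from the centre: 1,500 (Development and Training Phase). Internal validation: 500, no overlap with training (Internal Validation Phase; Definition and Source of Datasets).

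**1. The plan's own split.** 1,500 × 2/3 = 1,000 and 1,500 × 1/3 = 500. The stated 1,000/500 split reproduces exactly.

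**2. Are these the same patients?** Both places describe 1,500 retrospective patients from the study's own centre, with 400 obtained so far. The dataset section puts the remainder at 1,500 − 400 = 1,100. Nothing suggests a second centre cohort.

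**3. Overlap.** Minimum overlap = training n + validation n − available n.

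- Upstream training as written: 1,500 + 500 − 1,500 = 500, that is 500/500 = 100% of the internal validation set. Disjoint sets would need 1,500 + 500 = 2,000 centre patients.
- Upstream training limited to the 1,000: 1,000 + 500 − 1,500 = 0.
- External sets: these are described as data from outside the centre cohort, so the overlap is 0 of 3,000 and 0 of 10,000 under either reading.

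**4. Does the overlap reach the response model?** Yes. The microenvironment outputs are named as its inputs. The channel is limited, however. The upstream model is trained to identify, segment and quantify tissue features against physician annotation, and section 3.5 keeps the pathology annotators from seeing clinical outcomes. On that description, relapse or survival data of the 500 do not enter stage one.

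**5. Tuning and scoring.** Sections 3.1 and 3.4.1 both give the 500 the two jobs of estimating performance and tuning. The direction of the resulting bias is towards optimism. Its size depends on how many configurations are compared and how much they differ, and the protocol gives neither.

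**6. Order of events around the lock.**

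| Step | What the Protocol allows |
|---|---|
| External Set 1 | Calibration or limited optimisation, then the model is finalised |
| External Set 2 | Locked model, no adjustment; basis for the prospective studies |
| Prospective datasets | Optimisation named as a purpose (Part Two (2)) |
| Any time | Algorithm correction after subgroup findings (3.5) |

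The third row comes after the second by the protocol's own sequence. The fourth has no place in the sequence. No statement fixes which version enters the randomised trial.

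**The case against.** The strongest defence is that the 1,500 in the microenvironment section is shorthand. The response-model section also writes 1,500 under training and then carves out 500, and the dataset-definition section and 3.4.1 both give 1,000/500. That reading is possible, so this is an unresolved contradiction and not proof of a settled intention to train on everyone. It does not remove the problem. The microenvironment section is the only text specific to that model's training set. Section 3.4.1 justifies the 1,000 by the four treatment-response categories, which belong to the other model. One of the statements has to change.

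It is also fair that the internal evaluation is labelled preliminary, and that tuning on a development set before a locked external test is ordinary practice. That excuses the use of the 500 for tuning. It does not justify calling the set independent or reading its discrimination as unbiased.

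A reader might infer four stronger things that the documents do not support:

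- *That all validation figures are compromised.* They are not. Set 1 shares no patients with training; its figures are merely not a clean test of the model once it has been recalibrated on them. Set 2 is new data under an explicit lock, and a later change would not bias its estimate for the locked version.
- *That tuning on the 500 breaches the developer-access rule in 3.5.* That rule covers subsequent validation sets, and tuning is a declared purpose of the 500.
- *That the model is expressly frozen from Set 2 onward.* The no-adjustment rule is written for Set 2. The observational cohort's own description involves recording predictions and outcomes, not retraining, and fairness correction could be meant for Set 1. The fault is that this is left open.
- *That any later correction voids all 10,000 + 1,000 = 11,000 subsequent validation patients.* That holds only for a correction made after the observational cohort. One made between Set 2 and that cohort could still be tested on its 1,000 patients.

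**Conclusion.** The point holds for the internal validation set, and in a smaller form for the lock.

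Read literally, 500 of 500 internal-validation patients train the upstream model, against the protocol's own independence and no-leakage commitment. The same 500 both tune and score the response model. The internal figures are therefore likely optimistic. The size cannot be computed, and the upstream contribution may be modest because it runs through annotations. This rests on two assumptions: that the two descriptions of 1,500 centre patients refer to one cohort, which the matching counts support, and that the microenvironment section means what it says.

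On the lock, naming optimisation as a purpose of the prospective datasets and requiring fairness correction with no phase limit are not reconciled with finalising the model before Set 2. The consequence is a possible gap between the validated version and the one used in the randomised trial. The randomised comparison itself is not biased by this; what is lost is the link from the validation evidence to the tool being tested.

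**What to change.** 1. In 3.1, Part One (1), limit microenvironment training to public data plus the 1,000 training patients.
2. Tune the response model within the 1,000, for example by cross-validation, and score the 500 once. Otherwise, relabel the 500 as a tuning set and stop calling it independent.
3. Report External Validation Set 1 performance before any recalibration as the validation result, and treat what follows on that set as development.
4. In 3.1, Part Two (2), remove optimisation as a purpose of the prospective datasets. In 3.5, restrict fairness correction to before the lock. State that any post-lock change creates a new version that needs validation on unseen data, and that one fixed version is used in the randomised trial.

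The cost is mostly wording, and 1,100 of the 1,500 centre patients were still to be collected when the protocol was written. The real losses are 500 fewer cases for microenvironment training, and that fairness problems found after the lock wait for the next version.
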